## **12.0 SUBJECT WITHDRAWAL**

The subject is free to withdraw from this study at any time. The subject must inform the Investigator immediately if they intend to withdraw. To terminate the subject's participation in this study, they must contact the Investigator at the contact information listed on page one of the informed consent form. They will be asked to come to the study clinic or Investigators office to complete a final follow up visit and may be asked to perform end of study procedures. Their decision to participate in this study or to withdraw from this study will not influence the availability of their future medical care and will involve no penalty or loss of benefits to which they are otherwise entitled.

The Investigator in charge of the study can remove the subject from this study without their consent for any reason, including, but not limited to:

- a) His/her judgment that any condition or circumstance may jeopardize their welfare or the integrity of the study.
- b) Their failure to follow the instructions of the Investigator(s).
- c) If the study is stopped by the sponsor and/or Investigators participating in the study prior to completion.

Data collected prior to withdrawal will be used in data analysis but after withdrawal no further data will be collected.

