## **2.8 Post Treatment Procedures**

- Adverse events will be documented after treatment.
- Photographs may be taken post treatment.
- Clinician ease of use and subject treatment experience questionnaires may be performed.
- The following post treatment instructions will be reviewed:
  - Be careful not to expose area of treatment to external stimulation for at least 2 days after treatment.
    - Avoid ultraviolet rays and apply sunscreen.
    - Do not to scrub the skin or exfoliate for several days after treatment.
  - Refrain from high intensity exercise (such as running, weightlifting, aerobics), hot bath or saunas that may cause increase in skin temperature for 5 days after treatment.
  - Refrain from drinking alcohol or taking medicine that interferes with blood coagulation such as aspirin for 2 weeks after treatment.
  - If heat sensation or erythema (redness) after treatment is bothersome, use an ice pack to the treated area at home.
  - If the skin in the treatment area feels tight or dry, apply plenty of moisturizing cream, such as Neutrogena.
  - After the procedure, inflammation or edema (swelling) may block the pores and acne can temporarily worsen (about 7 days). If acne worsens, do not pick or squeeze as pigmentation changes may occur.
  - Sleep in a semi reclined position for the first 2-3 nights to minimize facial swelling.
  - Apply soothing facial mask as needed.

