#### 2.16.5 Analysis of Efficacy Variables

The primary efficacy variable is the change from baseline to visit 8 (30 days post last treatment) with respect to the treated condition evaluated by physician grading with CGAIS. Baseline is defined as the last assessment prior to the first treatment. The change from baseline to visit 8 will be analyzed using a Mixed Model Repeated Measures Analysis of Variance. A pairwise treatment group comparison at visit 8 will be performed using the results of this analysis. If a patient has no post-baseline assessment of the primary efficacy variable the patient data will be excluded from the statistical analysis of the improvement. Statistical significance with respect to the treatment group comparison at visit 8 will be declared if the two-sided p-value is < 0.05. For each treatment group summaries will be prepared for both the observed assessment and the change from baseline. Subject satisfaction results from Visit 9 will also be included in the summary. The summaries will include the sample size, mean, median, standard deviation, minimum, and maximum. Categorical variables will also include a summary which will include the number and percent of patients for each outcome. The statistical significance of the mean change from baseline for each treatment group will be determined using a student's paired t-test.

The secondary efficacy variables will be determined at a later date based on image grading. As with the primary efficacy variable the assessment at Visit 8 (30 days post last treatment) will be primary. The analysis and summaries for any secondary efficacy variables will be the same as that described for the primary efficacy variable. Statistical significance with respect to the treatment group comparison at visit 8 will be declared if the two-sided p-value is < 0.05.

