## 11.0 PREGNANCY

Females may not participate in this study if they are pregnant, breastfeeding, were pregnant within the last three months or are planning a pregnancy during the study.

If the subject thinks they have become pregnant during the study, it is important that they inform the Investigator immediately. If she becomes pregnant or thinks that she may be pregnant, she will be removed from the study and will be asked to perform a final evaluation similar to that of the final follow-up visit. The Investigator may request to track the pregnancy and will report the pregnancy to the Sponsor.

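### Section 12.0 stops all data collection at withdrawal and gives the final visit no day, so treated subjects who leave or are removed before Visit 8 can lack a valid primary grade even when willing to return

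*Combined protocol and SAP*

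**What the plan says.** Section 12.0 (Subject Withdrawal) asks a subject who withdraws to "complete a final follow up visit and may be asked to perform end of study procedures". No day is attached to that visit, and the end-of-study procedures are optional. The same section lets the investigator remove a subject: the investigator "can remove the subject from this study without their consent for any reason". It states no final visit for those subjects. It closes with one rule for everyone: "Data collected prior to withdrawal will be used in data analysis but after withdrawal no further data will be collected".

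Section 11.0 (Pregnancy) handles one kind of removal separately: "she will be removed from the study and will be asked to perform a final evaluation similar to that of the final follow-up visit". That evaluation is also undated.

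The analysis sections expect more. Section 2.16.5 places the primary CGAIS grade at Visit 8, 30 days after the last treatment, and 2.13 gives a window of one week either side. Section 2.16.3 makes the primary analysis intention-to-treat, counting everyone who starts treatment whether or not they finish, and leaves the missing-data method to be chosen later. Section 2.16.5 excludes a subject who has no post-baseline grade from the analysis of improvement. Section 2.16.1 requires investigator and subject satisfaction rates of at least 80%.

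Section 14.0 has adverse events followed until they resolve, settle or are explained, or until contact with the subject is lost. Section 2.15 requires follow-up to resolution.

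**The concern.** The plan commits to analysing all treated subjects at a fixed time after their last treatment, but its withdrawal rule prevents that measurement in those who leave. Visit 8 is counted from the last treatment actually received, and any number of treatments up to five is allowed (2.7, 2.9). Every treated subject who leaves early therefore has a well-defined Visit 8 date. Some would come in on that date if asked. The rule as written gives no means of asking them.

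Two things are at stake. First, a grade taken at an undated final visit may be used as if it were the 30-day result when it was taken much earlier. Second, if no grade is taken, the Visit 8 result and the satisfaction rate describe mainly those who stayed. Leavers may well be less satisfied, and in a single-group study judged against a fixed 80% threshold there is no comparison arm in which such a bias might partly cancel. There is also a safety consequence: an adverse event still open at withdrawal must be followed under 14.0 but may not be recorded under 12.0.

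**Working it through.** **Inputs.** Visit 8 window: 30 +/- 7 days, so days 23 to 37 after the last treatment (2.13). Treatment interval: 4 weeks +/- 2 weeks, so 14 to 42 days (2.7). Sample size: 120 including departures (2.16.2). Threshold: 80% (2.16.1). The figure of 120 comes with no effect size, standard deviation, power or dropout rate, so it cannot be reproduced. It is not disputed here.

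**Step 1: what each route out of the study provides.**

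| Route | Final visit stated? | Day after last treatment | Ratings |
|---|---|---|---|
| Stops treatment, stays in study | Yes, Visit 8 (2.9) | 23-37 | Scheduled |
| Subject withdraws (12.0) | Yes | Not stated | Optional |
| Removed by investigator, other than for pregnancy (12.0) | No | - | - |
| Removed for pregnancy (11.0) | Yes | Not stated | Like the final visit |

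The closing sentence of 12.0 makes no distinction among those who leave. If nothing may be collected after withdrawal, the requested final visit has to happen at or before it, or its data do not count. Section 11.0 adds to the difficulty because its evaluation is asked of a subject already removed.

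**Step 2: timing of an undated visit (illustration).** Assume that the final visit falls evenly over one treatment interval of L days after the last treatment. The share inside the Visit 8 window is max(0, min(L, 37) - 23) / L.

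- L = 14: 0/14 = 0%
- L = 28: 5/28 = 18%
- L = 42: 14/42 = 33%

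On this assumption 67% to 100% of such visits miss the window. The 0% for L = 14 follows from cutting the distribution off at day 14. The model also leaves out subjects who go after their last planned treatment.

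**Step 3: effect of lost ratings (illustration).** Assume m of 120 treated subjects have no rating, c = 120 - m have one, and the completers just reach the threshold with r = 0.8c rounded up. The all-treated rate then lies between r/120 (every missing rating a failure) and (r + m)/120 (every one a success). If missing counts as failure, reaching 80% of 120 takes 96 successes, so the completers need 96/c.

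| Assumed loss | m | r/c | All-treated range | Completer rate needed if missing = failure |
|---|---|---|---|---|
| 5% | 6 | 92/114 | 76.7%-81.7% | 84.2% |
| 10% | 12 | 87/108 | 72.5%-82.5% | 88.9% |
| 15% | 18 | 82/102 | 68.3%-83.3% | 94.1% |
| 20% | 24 | 77/96 | 64.2%-84.2% | 100% |

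For 10%: 87/120 = 72.5%, and (87 + 12)/120 = 82.5%. Every row straddles 80%. This takes the 80% criterion as read at Visit 8 in all treated subjects; 2.16.1 names no visit.

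**The case against.** The strongest reply is that the text is merely unclear. A reader might infer that the plan moves the final grade to the day of exit. No section says so. In this protocol the required follow-up visit is Visit 8, so the final visit in 12.0 could be read as exactly that visit. This stands as far as it goes: the timing is unstated, not set to exit. But reading it as Visit 8 puts it at odds with the bar on later data for anyone who withdraws before day 23, so the section needs correcting on either reading.

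A reader might also infer that anyone who stops treatment early loses Visit 8. They do not. A subject who stops treatment but stays in the study is covered by 2.9, and one who leaves after Visit 8 already has the primary grade. The problem is confined to those who leave or are removed before it.

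Nor do early leavers necessarily contribute nothing. Data from before withdrawal are used, the model is a repeated-measures one, and 2.13 schedules clinician questionnaires at treatment visits and at the one-week contact. If CGAIS was graded there, those grades can enter the model under a missing-at-random assumption. That is not assured. Section 2.8 describes the post-treatment clinician questionnaire as an optional one on ease of use, the one-week contact may be a telephone call, and 2.14 does not say at which visits CGAIS is taken. The satisfaction rate has no model behind it and no stated missing-data rule.

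It is tempting to add that early grades would fall in a period of expected worsening. The warning in 2.8 concerns acne only, and the study treats many other conditions, so it does not carry the argument.

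Finally, 2.1 calls this a feasibility study, dropout may be small, and some leavers will refuse any visit. All of that is fair and limits the weight of the point. It does not justify declining a grade from a subject willing to give it.

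**Conclusion.** The point holds as a defect in the follow-up rules. Section 12.0 bars data after withdrawal, does not distinguish leaving or removal from refusing further data collection, and gives its final visit neither a day nor required ratings. Section 11.0's evaluation is undated too, and other investigator removals have no stated visit. Against an intention-to-treat analysis at Visit 8, this leaves a missing or mistimed grade and satisfaction rating for subjects who go before that visit, including some who would have returned. It also contradicts the adverse event follow-up in 14.0 and 2.15.

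The size is unknown because the documents give no dropout rate and no exit timing. The figures above are bounds under assumed losses and show only that a modest loss is enough to leave the 80% criterion undecided: at 10% the range is 72.5% to 82.5%. They do not show that the trial's result would be wrong. The documents do not support a claim that exit grades replace Visit 8, or that all early leavers drop out of the analysis. The change is worth making because it is cheap and the lost data cannot be recovered afterwards.

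**What to change.** Amend 11.0 and 12.0 as follows.

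1. Limit the bar on further data to subjects who decline further contact, and record that refusal separately from the end of treatment or removal by the investigator.
2. Ask every other treated subject who leaves or is removed before Visit 8 to attend it at 30 days (+/- 1 week) after the last treatment received, with CGAIS, satisfaction and photographs. This need not extend to closure of the whole study by the sponsor (22.0), which would require sites to be kept running.
3. Keep the exit evaluation as a fallback, since for some subjects it will be the only contact. Have the ratings completed and the actual day recorded. Count it as Visit 8 only if taken on days 23-37; otherwise enter it as an earlier time point in the repeated-measures model.
4. Reconcile 12.0 with the adverse event follow-up in 14.0 and 2.15, so that it is clear what is recorded for an event still open when a subject leaves.

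The cost is a protocol and consent amendment, which needs IRB approval under 21.0, and some additional effort at sites to bring leavers back. The visit itself is already in the schedule. Some leavers will still not return, so a stated rule for missing grades and ratings remains necessary.

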#### **Physician Questionnaire:**

The Clinical Global Aesthetic Improvement Scale (CGAIS) ranging from "worse" to "very much improved" will be used to judge the improvement as seen by the treating Investigator.

Global Aesthetic Improvement Scale Assessment				
Rating	Description			
1	Very Much Improved- Optimal cosmetic result in this subject			
2	Much Improved- Marked improvement in appearance form the initial			
2	condition, but not completely optimal for this subject.			
2	Improved- Obvious improvement in appearance from initial condition, but a			
3	re-treatment is indicated.			
4	No Change- The appearance is essentially the same as the original condition.			
5	Worse- The appearance is worse than the original condition.			

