#### 2.16.3 Patient Populations

Interim results may be collected and reported. All data will be analyzed at the end of the study. The primary analysis will be performed by the intention-to-treat approach. Everyone who begins the treatment is part of the study whether he or she completes the study or not. Additional perprotocol analysis may also be performed on subjects who complete the entire clinical trial according to the protocol. The most appropriate method of handling missing values will be chosen based on the individual trial goals, endpoints and context.

The analysis of demographic, medical history, and efficacy variables will be based on all patients who are randomized and receive at least one treatment. The analysis of safety data will be based on all patients who are randomized, receive at least one treatment, and have at least some safety data.

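### Section 12.0 lets the open-label Investigator who grades the primary CGAIS remove subjects for any reason and then ends data collection, so Visit 8 results can depend on whom the rater removes

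*Combined protocol and SAP*

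**What the plan says.** **Removal (Section 12.0).** "The Investigator in charge of the study can remove the subject from this study without their consent for any reason". Three grounds are given as examples: (a) the Investigator's judgment about welfare or study integrity, (b) not following instructions, and (c) the study being stopped. The section closes: "Data collected prior to withdrawal will be used in data analysis but after withdrawal no further data will be collected".

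**Exit assessments.** Section 12.0 asks for a final follow-up visit in the paragraph on subjects who choose to leave. Section 11.0 asks for a final evaluation after removal for pregnancy. Neither is stated for removal under (a) or (b).

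**Analysis set (2.16.3).** "The primary analysis will be performed by the intention-to-treat approach", and "Everyone who begins the treatment is part of the study whether he or she completes the study or not". A per-protocol analysis is optional and additional, for "subjects who complete the entire clinical trial according to the protocol". On missing data: "The most appropriate method of handling missing values will be chosen based on the individual trial goals, endpoints and context".

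**Rater and endpoint.** The study is open label (2.2). The CGAIS "will be used to judge the improvement as seen by the treating Investigator" (2.14, Physician Questionnaire), and its Visit 8 value is the primary efficacy variable (2.16.5). The planned analyses are a mixed model for repeated measures and a paired t-test of mean change. Subjects with no post-baseline assessment of the primary variable are excluded.

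**Success (2.16.1).** Investigator and subject satisfaction rates must each reach 80%, and the side-effect profile must be acceptable. No denominator or visit is given for the rates.

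**The concern.** Intention-to-treat protects a result only if outcomes are sought from everyone who started treatment. Here the person who grades the primary outcome, knowing the treatment and seeing the skin at treatment visits, can also end its collection for a given subject. Non-adherence, which 2.16.3 leaves to an optional per-protocol analysis, is a listed ground for doing so.

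Only one treatment is described, so no comparator would reveal or offset selective loss. If the subjects removed tend to be poor responders, the mean CGAIS among those graded at Visit 8 looks better and the satisfaction rates rise towards the fixed 80% threshold. No improper intent is needed. Subjects who are disappointed may also be those who stop following instructions.

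**Working it through.** **Step 1. What happens to a subject removed under (a) or (b) before Visit 8**

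- *Is removal a withdrawal?* Section 2.12 speaks both of subjects who withdraw and of those who are withdrawn, and the no-further-data sentence in 12.0 comes after the Investigator's grounds. The natural reading is that it covers removals.
- *Is a final visit required?* Not clearly. The request in 12.0 is written for subject-initiated withdrawal, and the one in 11.0 for pregnancy.
- *Mixed model:* it can use any earlier post-baseline CGAIS. The schedule in 2.13 lists clinician questionnaires at treatment visits and at the 1-week contact, but does not say that they include CGAIS. Without an earlier CGAIS, 2.16.5 excludes the subject.
- *Paired t-test of change to Visit 8:* the subject has no Visit 8 value to contribute.
- *80% rates:* the outcome depends on the denominator, which 2.16.1 does not define, and on the missing-value method, which 2.16.3 leaves open.

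**Step 2. Possible size, for one satisfaction rate**

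Inputs from the plan: 120 subjects (2.16.2) and the 80% threshold (2.16.1). Assumptions: all 120 would otherwise be rated; the true rate is 75%; 5 subjects are removed, not replaced, and leave the denominator. The plan gives no removal rate and no expected satisfaction rate.

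Let X be the number satisfied among 120, X ~ Binomial(120, 0.75).

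- *None removed:* 0.80 × 120 = 96, so P(X ≥ 96) = 0.122.
- *5 removed:* 115 remain and 0.80 × 115 = 92 satisfied are needed among them. If d of the 5 are dissatisfied, 5 − d satisfied subjects are lost too, so the condition is X ≥ 92 + (5 − d).

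| Removed | Condition | Chance of reaching 80% |
|---|---|---|
| None | X ≥ 96 of 120 | 12.2% |
| 5 at random | at least 92 of 115, Binomial(115, 0.75) | 12.8% |
| 5, of whom 2 dissatisfied | X ≥ 95 | 17.2% |
| 5, of whom 3 dissatisfied | X ≥ 94 | 23.3% |
| 5, all dissatisfied (worst case) | X ≥ 92 | 38.2% |

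As a single example, 92/120 = 76.7% misses the threshold. The same 92 satisfied subjects out of 115 give 80.0%, which meets it.

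**Step 3. With removed subjects kept in the denominator**

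If removed subjects without a rating count as non-responders, 96 of 120 are again needed. When all 5 removed are dissatisfied, the chance returns to 12.2%.

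**The case against.** A reader might infer that Section 12.0 turns the promised intention-to-treat analysis into a per-protocol one. The documents do not support that. Removal from the study is not removal from the analysis set: 12.0 keeps data collected before withdrawal, 2.16.3 keeps everyone who began treatment, and the mixed model drops only subjects with no post-baseline score. Nor is it established that every removed subject lacks a Visit 8 rating. The final-visit request in 12.0 might be meant to reach Investigator removals, and the treatment-visit questionnaires might include CGAIS. These points stand, and they limit the finding to a possible loss rather than a certain one.

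The size can also be challenged. The 38% needs every removed subject to be dissatisfied and to leave the denominator; random removal changes almost nothing. Reaching 80% on one rate is not overall success, which also needs the other rate and an acceptable side-effect profile. The 120 includes departures, so full rating is not the plan's own baseline. Replacement is possible under 2.12, but needs prior sponsor and/or IRB approval. All of this stands too.

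Finally, 2.1 calls this a feasibility study and 3.2 says Investigator compensation does not depend on the outcome. Both reduce the weight of the point. Neither supplies a Visit 8 rating for a removed subject, and 3.2 itself acknowledges a risk of bias.

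**Conclusion.** The point holds in limited form. Followed as written, 12.0 allows the open-label rater of the primary variable to end outcome collection for a subject at discretion, and nothing clearly requires a Visit 8 assessment afterwards. The intention-to-treat set is preserved in name, but the Visit 8 paired t-test and, depending on the denominator, the 80% rates can vary with whom the rater removes. The mixed model is affected less if CGAIS is recorded before Visit 8, which the schedule leaves unclear.

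With 5 of 120 removed and a true rate of 75%, the chance of reaching 80% on one rate moves from 12% to between about 13% (random removal) and 38% (worst case), with 23% if 3 of the 5 are dissatisfied. These figures rest on removed subjects leaving the denominator without replacement. They illustrate sensitivity and do not predict what will happen. Nothing in the documents shows that removals would be selective. The change should be made because the loss is avoidable at low cost.

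**What to change.** Leave the Investigator's grounds for stopping treatment as written, and change the following.

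1. **Section 12.0:** separate stopping study treatment from ending follow-up. Replace the no-further-data sentence with wording to this effect: subjects removed by the Investigator under (a) or (b) who still consent are asked for the Visit 8 CGAIS, satisfaction rating and photographs, or for the final follow-up visit already described; data collection stops only when consent is withdrawn, the subject is lost to follow-up or the study is stopped.
2. **Section 11.0:** reconcile the removal for pregnancy and its final evaluation with the new wording.
3. **Section 15.0:** record non-adherence as a protocol deviation, so that it affects only the per-protocol analysis.
4. **Sections 2.16.1 and 2.16.3:** keep all treated subjects in the denominator of the 80% rates, and state before results are seen how missing ratings are handled. Add a sensitivity analysis counting removed subjects without a Visit 8 rating as non-responders.
5. **Reporting:** list Investigator removals by centre, with the reason and the last rating.

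The cost is rewording of these sections, one sensitivity analysis, one listing and a few visits that the schedule already contains. The rates may come out slightly less favourable.

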## 2.15 Adverse Event Recording

All data captured must be supported by the Investigator's timely assessment and documentation of the adverse event in the case report forms or source documents. All documented adverse events will be reviewed by the Sponsor or designee to determine whether the adverse event meets regulatory reporting requirements and to ensure timely adverse event reporting to meet local and global regulatory requirements. All adverse events must be followed until their resolution.

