#### 14.0 ADVERSE REACTIONS DEFINITIONS AND REPORTING REQUIREMENTS

All adverse events that occur, starting from the time of the first treatment, will be recorded in the source documents and Case Report Forms (CRF).

Adverse Events (AE) occurring will be captured and followed until the condition resolves, stabilizes, is otherwise explained, or the subject is lost to follow-up. Subjects will be instructed that they may contact the Investigator at any time throughout the course of the study.

The Investigator and/or designated study staff will review each event and assess its relationship to the study device (not related, unlikely, possible, probable, and highly probable). The following definitions will be used for rating relationship to the PotenzaTM treatments:

- Not related The event is clearly related to other factors such as the subject's clinical state, therapeutic interventions, or concomitant medications administered to the subject.
- Unlikely The event was most likely produced by other factors such as the subject's clinical state, therapeutic interventions, or a concomitant medication administered to the subject; and does not follow a known response pattern to the investigational product.
- Possible The event follows a reasonable temporal sequence from the time of investigational product administration; **and/or** follows a known response pattern to the study sampling sessions; **but** could have been produced by other factors such as the subject's clinical state, therapeutic interventions, or concomitant medications administered to the subject.
- Probable The event follows a reasonable temporal sequence from the time of investigational product administration; **and** follows a known response pattern to the investigational product; **and** cannot be reasonably explained by other factors such as the subject's clinical state, therapeutic interventions, or concomitant medications administered to the subject.

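### Section 12.0 stops data collection at withdrawal with no exception for open adverse events, which contradicts the follow-up rules in sections 2.15 and 14.0

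*Combined protocol and SAP*

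**What the plan says.** Section 12.0 covers two kinds of exit. A subject may withdraw at any time, and is then asked to come in to "complete a final follow up visit and may be asked to perform end of study procedures". Separately, "The Investigator in charge of the study can remove the subject from this study without their consent for any reason"; the first example given is a condition or circumstance that may put the subject's welfare at risk. The section then closes with a single data rule: "Data collected prior to withdrawal will be used in data analysis", but "after withdrawal no further data will be collected".

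The adverse event sections set a different rule. Section 2.15 states: "All adverse events must be followed until their resolution". Section 14.0 says that events will be "followed until the condition resolves, stabilizes, is otherwise explained, or the subject is lost to follow-up", and later repeats these four end points for serious and non-serious events alike.

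Section 11.0 removes a subject who is, or thinks she may be, pregnant. It asks her for a final evaluation and adds: "The Investigator may request to track the pregnancy and will report the pregnancy to the Sponsor".

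**The concern.** Safety is the first primary objective in section 1.2, and section 2.16.1 makes success depend partly on a side effect profile that the physician finds acceptable. The possible effects listed in section 2.15 include scarring, hypopigmentation, hyperpigmentation and textural irregularity. For effects of that kind, whether they persist is a large part of the safety result.

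Two of the five centers could treat the same subject differently. One, applying section 12.0, closes the record with the event open. The other, applying section 2.15 or 14.0, keeps in contact until the outcome is known. Neither has departed from the protocol as it reads its own section, and nothing says which section prevails. If subjects tend to exit because of an adverse event, the missing outcomes would not be a random subset. An outcome that was never collected cannot be recovered at analysis.

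**Working it through.** The point rests on no sample size, power or event count, so no formula applies. The check sets the sections side by side and asks what a site must do with an event still open at exit.

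| Section | Rule | Exception for withdrawal or removal |
|---|---|---|
| 12.0, last sentence | Use data from before withdrawal; collect none after it | None for open adverse events |
| 2.15 | Follow every adverse event to resolution | None |
| 14.0 (stated twice) | Follow to resolution, stabilization, another explanation, or loss to follow-up | None |
| 12.0, subject's own withdrawal | Final visit requested | Not applicable |
| 12.0, removal by the investigator | No final visit stated | Not applicable |
| 11.0, removal for pregnancy | Final evaluation requested; pregnancy may be tracked | Not applicable |

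**Step 1: can the rules be met together?** Take an event that has neither resolved nor stabilized, has no other explanation, and belongs to a subject who can still be reached. On the ordinary meaning of the term (the documents do not define it), that subject is not lost to follow-up. Section 14.0 therefore requires contact to go on, as does section 2.15. Section 12.0 forbids further collection. Both cannot be met. Sections 2.15 and 14.0 also differ from each other, since section 2.15 names resolution alone.

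**Step 2: does the section 12.0 rule reach removed subjects?** Its last sentence says only withdrawal, and the section uses different verbs for the subject's act and the investigator's. But the sentence closes a section headed Subject Withdrawal and follows the list of removal grounds, and section 2.12 speaks both of subjects who withdraw and of those who are withdrawn. The wider reading is plausible but not explicit. On the narrower reading, section 12.0 has no data rule for removed subjects, which also needs repair.

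**Step 3: does the final visit close the gap?** Only in part. It is requested in the text on the subject's own withdrawal. It is one visit, so an event open on that day remains open. Section 12.0 does not say whether data from a visit held after the date of withdrawal may be used.

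**Step 4: pregnancy.** Tracking a pregnancy after removal is data collection after removal, and section 14.0 lists birth defect among the serious outcomes. This fits badly with the last sentence of section 12.0 if that sentence covers removal.

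**Step 5: what is lost?** Leaving aside its mention of randomization, which section 2.2 does not describe, section 2.16.3 puts in the safety analysis every treated subject with some safety data. Events recorded before exit therefore count. At risk are the final outcome of events open at exit, and events that first arise afterwards.

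**Step 6: how many subjects?** The planned total in section 2.16.2 is 120, including departures. No rate of withdrawal, removal or unresolved events is given, so the number affected cannot be derived.

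**The case against.** The strongest reply is that this is a wording slip with little effect. Data from before withdrawal are kept, so a burn recorded before exit stays in the tables with its severity and relatedness. A subject who intends to withdraw is asked for a final visit, which can be read as the last step of the exit, with event status recorded there. Stopping treatment is not withdrawal: section 2.7 allows up to five treatments as the investigator determines, and a subject who stops early can stay enrolled and attend the 30-day visit. No section makes an adverse event a trigger for removal. The pregnancy provision is specific and optional and can stand beside a general rule. The study is an open-label feasibility study, and section 2.16.6 plans only counts and percentages for safety.

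Most of this stands, and it limits the point. It does not remove the conflict for a subject who exits fully with an event open, least of all one whom the investigator removes.

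Three stronger inferences are tempting, and the documents support none of them:

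- **That harmed subjects drop out of the safety data.** Sections 12.0 and 2.16.3 keep them in.
- **That the reported profile will look more benign than it is, by some stated amount.** The documents give no exit rate and no onset times for late effects. Section 14.0 has outcome categories for unchanged, worse, unknown and lost to follow-up. An open event becomes a non-persistent one only if unknown is counted as resolved, and no section says to do that. Any worked rate would rest on invented counts.
- **That section 12.0 expressly ends collection for removed subjects.** That is a reading, as step 2 shows.

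**Conclusion.** Wrong as written: the protocol contradicts itself. For an adverse event open at exit, section 12.0 cannot be followed together with sections 2.15 and 14.0. Following section 12.0 as worded gives up outcome data on a primary objective. The loss is confined to final outcomes of open events and to events arising after exit. Its extent cannot be estimated, and its direction is only a possibility: persistent harm would be understated if exits are related to harm and unknown outcomes are not shown as such.

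The contradiction needs no assumption about rates. It assumes only that a subject who has left but can be reached is not lost to follow-up. Its extension to removed subjects rests on the wider reading of the last sentence of section 12.0.

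**What to change.** Replace the last sentence of section 12.0 with a rule that says:

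- Data collected up to withdrawal, and data from the final visit or evaluation requested in sections 11.0 and 12.0, are used in the analysis.
- After withdrawal from treatment or removal by the investigator, adverse events, and any pregnancy being tracked, continue to be followed to the section 14.0 end points. Collection stops earlier only if the subject withdraws consent to follow-up, and that date is recorded.
- The rule states until when newly arising events are recorded for such a subject.
- Events still open when follow-up stops are reported as unresolved or unknown, never as resolved.

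Reconcile sections 2.15, 11.0, 12.0 and 14.0 to this one rule, including the difference between 2.15 and 14.0 on end points, and add a matching sentence to the consent form. State in section 12.0 whether a final visit is also requested of subjects the investigator removes.

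The change concerns data collection, not treatment, and leaves the subject's right to leave intact. It costs one protocol paragraph, one consent sentence and a few extra calls or visits for subjects who exit early. The reported side effect profile may become slightly less favorable.
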